17.4. Procedure for Accounting for Missing, Unused, and Spurious Data

Completion (imputation) of data deficiencies is not expected. For each variable analysed, the number and percentage of missing data in each category will be provided.

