17.1. Description of Statistical Methods

Nominal and ordinal scale data will be presented as counts (N) and percentages (%) in each of the categories analysed, with the denominator used to determine the percentages given.

The range of summaries for interval scale variables, in each of the categories analysed, will include: mean with standard deviation, median and lower and upper quartile, maximum and minimum value, as well as the number of people for whom estimates of basic statistics were made.

If graphical presentation of the data is necessary, box-plots (median, quartiles, range of outliers or minimum/maximum values) and/or graphs of averages with 95% confidence intervals will be used.

The distribution of the variables will be evaluated based on the quantile-quantile (Q-Q) plot and the results of the Shapiro-Wilk test. Homogeneity of variance will be assessed using Levene's test.

For the CRS-R and MOCA tests, and the C-Eye X MCSD and CFA tests, the results will be presented as:

- 1) the sum of scores for all subscales of the test,
- 2) the point value obtained in each subscale,
- 3) the percentage of the total score for all subscales of the test related to the maximum value possible for the test (23 points for the CRS- R test, 30 points for the MOCA test, 11 points for the MCSD test, 24 points for the CFA test),
- 4) the percentage value in each subscale related to the maximum value possible in the subscale.

In each subsequent visit following visit 1, the relative percentage increases in total and subscale scores will be shown for visit 1. In addition, from all consecutive visits, the sum total of the test and subscale scores for each test will be determined; the data will be presented as raw values (points) and percentages related to the sum total of the maximum possible value for the test/subscale.

Analysis of the results of each test over time (in 3 or 5 consecutive visits) will be carried out using analysis of variance with repeated measures and contrast analysis (for raw or transformed data) or Friedman analysis of variance – depending on the type of data distribution, for both raw data and transformed percentages.

For patients enrolled in Test 1, the percentages of total scores for all subscales of the test relative to the maximum value possible in the test will be used to compare the scores during the

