follow-up period (in 5 consecutive visits) obtained by the MCSD C-Eye X test with those of the CRS-R test. The analysis will be conducted using one-way analysis of variance (the type of test will be a factor) with repeated measures and contrast analysis. If the assumptions of normality of distribution are not met, an appropriate nonparametric method or logarithmic transformation or aligned rank transformation will be used. The relative percentage increases in total scores at the last visit relative to the Visit 1 and the summed (from all measurements over time) total scores relative to the summed maximum possible on a given test (%) will be compared using Student's t-test or Mann-Whitney U-test, depending on the type of data distribution.

For patients enrolled in Test 2, the percentages of total scores for all subscales of the test related to the maximum value possible in the test will be used to compare the results during the follow-up period (in 3 consecutive visits) obtained with the CFA C-Eye X test with the results of the CRS-R and MOCA tests. The analysis will be conducted using one-way analysis of variance (the type of test will be a factor) with repeated measures and contrast analysis. If the assumptions of normality of distribution are not met, an appropriate nonparametric method or logarithmic transformation or aligned rank transformation will be used. Relative percentage increases in total scores at the most recent visit relative to the Visit 1 and the summed (from all measurements over time) total scores relative to the summed maximum possible on a given test (%) will be compared using one-factor analysis of variance (the type of test will be a factor) with Tukey's post-hoc test or Kruskal-Wallis one-factor analysis of variance, with multiple comparisons tests of mean ranks for all samples, depending on the type of data distribution.

Passing-Bablok orthogonal regression will be used to evaluate the consistency of test scores (summed percentages of total scores for all subscales of the test related to the maximum possible value for the test) of the MCSD and CFA C-Eye X with the CRS-R and MOCA tests. In addition, Pearson's linear correlation coefficient or Spearman's rank coefficient will be determined depending on the distribution of the data. If the assumptions of normality of distribution are not met, an appropriate nonparametric method or logarithmic transformation will be used.

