17.6. Inclusion in Analysis

The results of all patients who participate in the Minimal Consciousness Detection Test (Test 1 – MCSD) and the Cognitive Function Examination Test (Test 2 – CFA) will be included in the analysis.

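### With no imputation, the repeated-measures ANOVA and Friedman analyses in 17.1 in their standard form omit any patient who missed a visit, which does not fit the all-participants rule in 17.6

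*Protocol*

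**What the plan says.** Four parts of the protocol bear on who enters the repeated-measures analyses.

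- **Section 17.1, change over time.** "Analysis of the results of each test over time (in 3 or 5 consecutive visits") is to use "analysis of variance with repeated measures and contrast analysis (for raw or transformed data) or Friedman analysis of variance", depending on the distribution.
- **Section 17.1, comparison of instruments.** For MCSD against CRS-R, and for CFA against CRS-R and MOCA: "The analysis will be conducted using one-way analysis of variance (the type of test will be a factor) with repeated measures and contrast analysis". Scores summed over all visits are also expressed as a percentage of the summed maximum. They feed further comparisons and the Passing-Bablok regression.
- **Section 17.4.** "Completion (imputation) of data deficiencies is not expected". Counts and percentages of missing data are to be reported.
- **Section 17.6.** "The results of all patients who participate in the Minimal Consciousness Detection Test (Test 1 – MCSD") and in Test 2 are to be included in the analysis.

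Section 4 foresees incomplete participation. It aims at 90 analysed observations (45 per test), allows replacement of up to 10%, and accepts 10% dropout with a minimum of 81. Section 7 says that a Test 1 observation lacking any one required element does not count as fully completed, but not whether it is then analysed. Levene's test is the only variance check that 17.1 names, and the choice of methods is to be discussed further in the statistical analysis plan.

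**The concern.** Classical repeated-measures ANOVA and Friedman's test both need a full row of visits for each patient. Without imputation, a patient with four of five sessions contributes nothing to them, although four valid measurements exist and 17.6 says that the patient's results are included. Patients with severe brain injury who miss a session may differ from those who do not. The complete rows could then be a selected subset, and a smaller one.

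The summed score has a related gap. If a visit is missing, 17.1 does not say whether the denominator covers the planned visits or the visits done. With planned visits, a missed session counts as a score of zero.

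A lesser matter concerns the F test itself. The uncorrected repeated-measures F test rests on sphericity (equal variances of the within-patient differences), and Levene's test does not examine that.

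**Working it through.** **The plan's own figure.** Section 4: 90 × (1 − 0.10) = 81, as stated. The replacement cap is 0.10 × 90 = 9. Section 17.2 gives no statistical basis for the 90, so there is no power calculation to reproduce.

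**Complete cases.** Inputs: 45 patients per test and 5 or 3 visits (sections 4 and 17.1). The per-visit missed rate *m* is an assumption, taken as independent across visits and before make-up sessions or replacement. Expected complete patients = 45 × (1 − *m*)^5 for Test 1 and 45 × (1 − *m*)^3 for Test 2.

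| *m* (assumed) | Test 1 | Test 2 | Total | Lost, Test 1 / Test 2 |
|---|---|---|---|---|
| 1% | 42.8 | 43.7 | 86.5 | 4.9% / 3.0% |
| 2% | 40.7 | 42.4 | 83.0 | 9.6% / 5.9% |
| 5% | 34.8 | 38.6 | 73.4 | 22.6% / 14.3% |
| 10% | 26.6 | 32.8 | 59.4 | 41.0% / 27.1% |

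Test 1 stays within a 10% loss only if *m* ≤ 1 − 0.9^(1/5) = 2.1%.

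**Summed score.** Take a patient who scores 6 of 11 on the MCSD at four visits and misses the fifth. Over planned visits the result is 24/55 = 43.6%. Over visits done it is 24/44 = 54.5%.

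**Sphericity.** Simulation with n = 45, no true visit effect, equal variances, nominal 5% and 8,000 runs per setting. The AR(1) correlations are assumed.

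| | ρ = 0.5 | ρ = 0.7 | ρ = 0.9 |
|---|---|---|---|
| 5 visits, uncorrected F | 5.6% | 6.9% | 8.2% |
| 5 visits, Greenhouse-Geisser | 4.1% | 4.8% | 5.0% |
| 3 visits, uncorrected F | 5.4% | 5.1% | 5.8% |

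A last-versus-first contrast with its own error term stayed between 4.4% and 5.3% throughout. On the same 5-visit structure (3,000 runs), Levene's test rejected in 1.8% of runs at ρ = 0.7 and 0.2% at ρ = 0.9, so it does not detect this departure.

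**The case against.** The protocol never prescribes listwise deletion. Having no imputation is compatible with a likelihood-based analysis in the statistical analysis plan, and descriptive summaries can include everyone, so 17.6 can be met in part. This stands as a limit on the claim: the loss concerns the ANOVA and Friedman analyses in their standard form, which are the methods that 17.1 names.

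The missed rates are assumptions, and the schedule has slack. With a gap of one day, five sessions span about 9 days of a 15-day window, and three span about 5 of 14, so some missed sessions can be made up. Up to nine patients may be replaced. All this stands and can reduce the loss. Replacement, however, puts a completer in place of a non-completer, which restores the number but not the representativeness.

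The denominator of the summed score may be meant as measurements taken. The wording allows that reading, but does not fix it.

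A reader might go further and infer that the study's error bars are wrong, or that Levene's test is a mistaken check. The documents do not support either. The planned 95% intervals are for means and do not rest on sphericity, nor do contrasts with their own error term. MCSD against CRS-R has two levels, so that main effect has no sphericity issue. Section 17.1 also names t-tests and one-factor ANOVA, where Levene's test is a usual check, and a sphericity correction can be left to the statistical analysis plan. Contrast error rates of about 10% (CFA against MOCA) and 1% (CRS-R against MOCA) can be simulated for Test 2, but only with pooled-error contrasts, which the protocol does not specify, and with assumed standard deviations of 25, 15 and 5 points.

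**Conclusion.** The point holds for the analysed sample. Taken at their standard meaning, 17.1 and 17.4 give a complete-case analysis that does not fit 17.6, and section 7 leaves open what happens to an incomplete Test 1 observation. How much this costs depends on a rate that the protocol does not give. It is modest at 2% missed per visit (83 of 90 complete). At 5% it takes the total to about 73, below the protocol's minimum of 81, before any make-up or replacement. The summed score is ambiguous by 10.9 percentage points in the example (54.5 − 43.6).

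Non-sphericity is a secondary matter. It can raise the uncorrected 5-visit F test to about 6–8% under the assumed correlations, and has little effect with 3 visits. It would not be a finding against the protocol by itself, but the same change of method removes it.

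**What to change.** 1. **Section 17.1.** Make the main repeated-measures analysis a likelihood-based linear mixed model on percentage scores, with fixed effects for instrument, visit and their interaction. Use all observed visits, Kenward-Roger degrees of freedom and an unstructured within-patient covariance over visits and instruments. Take the contrasts from this model.
2. **Fallback covariance.** An unstructured matrix has 10 × 11 / 2 = 55 parameters in Test 1 (2 instruments × 5 visits) and 9 × 10 / 2 = 45 in Test 2 (3 × 3), with about 45 patients each, so it may not converge. State a fallback in advance that allows unequal variances and serial correlation. Random patient and patient-by-instrument intercepts with independent residuals are not enough. They impose compound symmetry over visits, and with complete data on one instrument they return the uncorrected ANOVA F for visit.
3. **Summed score.** Express it as a percentage of the maximum over the visits at which all the compared instruments were done.
4. **Sections 17.4 and 17.6.** State that all observed visits of all participants enter, including Test 1 observations that section 7 does not count as fully completed.
5. **Levene's test.** Keep it for the between-group tests only.

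The cost is protocol and analysis-plan wording and standard software, with no new data. The downside is that the model assumes data are missing at random, which should be stated.

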17.5. Procedures for Reporting any Deviation(s) from the Original Statistical Plan

Not applicable

17.6. Inclusion in Analysis

The results of all patients who participate in the Minimal Consciousness Detection Test (Test 1 – MCSD) and the Cognitive Function Examination Test (Test 2 – CFA) will be included in the analysis.

18. ACCESS TO SOURCE DATA/DOCUMENTS

Authorised representatives of the Sponsor, the facilities where the Study will be conducted, as well as the monitoring bodies, will have direct access to the collected data.

19. QUALITY CONTROL AND QUALITY ASSURANCE PROCEDURES

The Study will be conducted in accordance with the currently approved study protocol, the approval of the Ethics Committee of the Academy of Physical Education in Wroclaw (approval number 11/2022) and the Helsinki Declaration, as well as the regulations and standard operating procedures of Poland and Germany.

The Study will conduct regular monitoring of the procedures and manner of data collection, as well as its compliance with the assumptions and source documents.

Monitors will verify this and how the study is conducted and that data is generated, documented and reported in accordance with applicable legal requirements.

20. ETHICS

Prior to the Study, approval was obtained from the Senate Committee on Research Ethics at the Academy of Physical Education in Wroclaw (approval no. 11/2022; date: 28.03.2022).

20.1. Approvals

The Study has received appropriate ethics committee approvals and is conducted in accordance with the Declaration of Helsinki.

20.2. Participant Confidentiality

The Study team will ensure that the anonymity of the Subjects is maintained. Patients will be identified by code – the participant’s identification number on the Clinical Observation Card (CRF) and in the C-Eye X system.

All documents will be securely stored and accessible only to authorised representatives of the Sponsor, the facilities where the study will be conducted, as well as monitoring authorities.

The Study software environment, which is the responsibility of the external CRO, will be installed on a server infrastructure that provides security in accordance with ISO 27001.

21. DATA HANDLING AND RECORD KEEPING

The data collected will be sent electronically directly to a medical data collection platform that ensures information security in accordance with ISO 27001. Supervision of the security of the collected data will be performed by a CRO selected by the Sponsor that specialises in conducting such projects.

22. FINANCING AND INSURANCE

The research is co-financed under the National Research and Development Centre’s competition 2/1.1.1/2020 grant application number: POIR.01.01.01-00-2125/20.

Insurance for patients included in the Study is provided by the Sponsor.

23. PUBLICATION POLICY

Publication of the results obtained in the Study will be carried out in accordance with the principles of good ethics in scientific research and the relevant requirements of scientific journals.

APPENDIX A: SCHEDULE OF PROCEDURES**Test 1: Minimally Conscious State Detection Test (MCS D Test)**

Procedures	Screening	Visit 1	Visit 2	Visit 3	Visit 4	Visit 5	Final Visit
Informed consent, Medical history, Physical examination, Eligibility criteria	x						
CRS-R		x	x	x	x	x	
C-Eye X		x	x	x	x	x	
Completion of data in eCRF + uploading results from C-Eye X to online repository (after the visit)	x	x	x	x	x	x	x
Physical examination, Compliance with protocol, Adverse event							x

Test 2: Cognitive Function Assessment Test (CFA Test)

Procedures	Screening	Visit 1	Visit 2	Visit 3	Final Visit
Informed consent, Medical history, Physical examination, Eligibility criteria, etc.	x				
CRS-R		x	x	x	
MOCA test		x	x	x	
C-Eye X		x	x	x	
Completion of data in eCRF + uploading results from C- Eye X to online repository (after visit)	x	x	x	x	x
Physical examination, Compliance with protocol, Adverse event					x

APPENDIX B: C-Eye X TEST RESULTS TABLES

Test 1: Minimally Conscious State Detection Test (MCS D Test)

Detekcja minimalnej świadomości – podsumowanie wyników

Pomiar 1 Pomiar 2 Pomiar 3 Pomiar 4 Pomiar 5 Podsumowanie

1. Wrażliwość słuchowa					
1.1. Słuchowy odruch wzdrygnięcia					
2. Funkcje wzrokowe					
2.1 Fiksacja					
2.2 Śledzenie wzrokowe					
2.3 Gnozia wzrokowa					
3. Integracja słuchowo-wzrokowa					
3.1. Rozpoznawanie bodźców słuchowych – kolor					
3.2. Rozpoznawanie bodźców słuchowych – mono					
4. Wykonywanie poleceń					
4.1. Wskazywanie przedmiotu					
4.2. Wskazywanie części ekranu					
5. Orientacja autopsychiczna					
5.1. Imię					
5.2. Rok urodzenia					
6. Próba lokalizowania ucisku					
6.1. Reakcja na ucisk					
					Diagnoza pacjenta

Test 2: Cognitive Function Assessment Test (CFA Test)

Badanie funkcji poznawczych – podsumowanie wyników

Pomiar 1 Pomiar 2 Pomiar 3 Podsumowanie sekcji

1. Uwaga			
1.1. Śledzenie wzrokowe			
1.2. Wygaszanie wzrokowe			
1.3. Test hamowania odruchów wzrokowych			
1.4. Łączenie elementów (1)			
1.5. Łączenie elementów (2)			
1.6. Lokalizowanie pól			
2. Funkcje językowe			
2.1. Rozpoznawanie przedmiotów (obrazy 3D)			
2.2. Rozpoznawanie przedmiotów (zdjęcia)			
2.3. Rozumienie zdań (figury)			
2.4. Czytanie (słowa)			
2.5. Pisanie (wyrazy)			
3. Funkcje wzrokowo-przestrzenne			
3.1. Porównywanie kształtów			
3.2. Rozpoznawanie perspektywy			
3.2. Wzrokowe rozpoznawanie emocji			
4. Orientacja autopsychiczna			
4.1. Imię			
4.2. Rok urodzenia			
5. Pamięć			
5.1. Orientacja w czasie			
5.2. Wzrokowa pamięć krótkotrwała (kształty)			
5.3. Wzrokowa pamięć krótkotrwała (litery)			
5.4. Wzrokowa pamięć krótkotrwała (film)			
6. Myślenie abstrakcyjne			
6.1. Rozpoznawanie sekwencji			
6.2. Klasyfikowanie przedmiotów			
6.3. Rozpoznawanie liczebności			
6.4. Brakująca figura			
Podsumowanie pomiarów			Wynik ogólny

Appendix 2

ADVERSE EVENT REPORT FORM

Fill out the form and email it to [contact] or call [contact]

Patient information		
Patient ID:		Date of birth (DD-MM-YYYY): ____ - ____ - _____
Body height (cm):	Body mass (kg):	Sex:  M  F
Information about the adverse event		
Report type:  Primary report  Follow-up report		
Date of obtaining information about the event (DD-MM-YYYY) ____ - ____ - _____		
Date the event occurred (DD-MM-YYYY): ____ - ____ - _____	Date the event ceased (DD-MM-YYYY): ____ - ____ - _____  The event is still ongoing	
Description of adverse event:		
Event classification		
 Severe adverse event		
 Death, date (DD-MM-YYYY): ____ - ____ - _____		
 Threat to life		
 Permanent or significant disability or impairment		
 Hospitalisation/extension of it date from: ____ - ____ - _____  continues		
 Other medically relevant		
 Non-serious adverse event		

Linking an adverse event to C-Eye X:  definitely related  high probability of relation  likely related  doubtful relation  unrelated	Justification for linking the event to C-Eye X:
Event outcome:  recovery  recovery with permanent consequences  under treatment  no successful treatment  fatal  unknown	
Additional information (laboratory tests, medical history, etc.): 	

Information on the reporting person

First name:	Surname:
Email address:	Phone number:
Signature:	Date of the report (DD-MM-YYYY): ____ - ____ - ____
